### 9.3.1. Treatment-emergent Adverse Events

An AE will be regarded as treatment-emergent if it was present prior to receiving the first injection of rFIXFc and subsequently worsened in severity, or was not present prior to receiving the first injection but subsequently appeared before the patient’s last visit on study or the follow-up phone call, whichever came later (or the date of withdrawal/loss to follow-up).

The algorithm for the determination of treatment emergence when an onset date is partially or completely missing is described below.

- If the onset time of an adverse event (if time is collected) is missing and the date of onset is the date of dosing, the AE is considered to be a TEAE.
- If the onset day of an adverse event is missing and the month and year of the onset of the AE are either the same or later than the month and year of the first treatment, the AE will be considered a TEAE.
- If the onset day of an adverse event is missing and the month and year of the onset of the AE precede the month and year of the first treatment, the AE will not be considered a TEAE.
- If the onset month of an adverse event is missing and the year of the onset of the AE is either the same as or later than the year of first treatment, then the AE will be considered a TEAE.
- If the onset month of an adverse event is missing and the year of AE onset precedes the year of first treatment, the AE will not be considered a TEAE.
- If the onset day, month, and year of an adverse event are missing, the AE will be considered to be a TEAE.
- If start date is partial but the stop date can be determined to be before the start of the first dose of study drug, then the AE will not be considered a TEAE.

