15.3. Monitoring and Recording Events

15.3.1. Adverse Events

Any AE experienced by the subject between the time of signing of the ICF and the Safety Follow-up Visit is to be recorded on the eCRF, regardless of the severity of the event or its relationship to study treatment.

All AEs experienced by the subject should be followed up until they have resolved, stabilized, or returned to baseline in subsequent visits.

Any adverse event that occurs after the first dose of commercially available rFIXFc but prior to signing of the ICF should be reported as a post-marketing event; such an event will not be recorded in the eCRF.

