## **3.3. Sample Size Justification**

The planned total sample size for this study is approximately 30 patients.

Because the size of the hemophilia population is limited, the sample size is based on clinical rather than statistical considerations. Taking into account the CHMP Guideline and in an effort to enroll a sufficient number of patients to assess the efficacy and safety of rFIXFc in this population of primarily very young children, approximately 30 patients will be enrolled to achieve at least 20 patients with no less than 50 EDs by the completion of the study.

	Statistical Analysis Plan	Final v1.0
---	----------------------------------	-------------------

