### **5.5. Handling of Missing Data**

Aside from the following, no imputation of study data will be performed.

The occurrence of a new bleeding episode will be imputed if >72 hours lapse between 2 consecutive injections administered to treat bleeding. Details are provided in Section 7.4.1.

For the analysis of AEs and concomitant medications/procedures, if the stop/start date of an AE/concomitant medication is missing or partial, the corresponding study day will be left blank. However, inferences will be made from the partial and missing dates to classify medications as prior and/or concomitant and AEs as treatment emergent (or not). These inferences are described in Sections 6.4.1 and 9.3.1, respectively.

For patients in the ITI Subgroup, determination of response requires baseline IR. If this is missing, an absolute value is employed. Further details can be found in Section 7.4.9.

	Statistical Analysis Plan	Final v1.0
---	----------------------------------	-------------------

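### SAP 9.3.1 counts an adverse event with a completely missing onset date as treatment-emergent even when it is known to have ended before the first dose

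*SAP*

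**What the plan says.** SAP 9.3.1 opens with a definition. An AE is treatment-emergent (a TEAE) if it was present before the first injection of rFIXFc and then worsened, or if it "was not present prior to receiving the first injection but subsequently appeared before the patient’s last visit on study" or the follow-up call.

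A list of rules for incomplete onset dates follows, introduced by this sentence: "The algorithm for the determination of treatment emergence when an onset date is partially or completely missing is described below". Three features of the list matter here.

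- If day or month is missing, the recorded part of the date is compared with the date of first treatment. The same or a later period means TEAE; an earlier period means not a TEAE.
- If nothing is recorded, the rule is unconditional: "If the onset day, month, and year of an adverse event are missing, the AE will be considered to be a TEAE".
- The last rule is the only one that uses the stop date. It begins "If start date is partial but the stop date can be determined to be before the start of the first dose of study drug", and its result is that the AE is not a TEAE.

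SAP 5.5 refers to 9.3.1 for these inferences and adds no rule of its own for a completely missing onset.

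**The concern.** The introductory sentence names partial and complete missingness as two separate cases, and the list gives the second its own rule. The stop-date exclusion is then written for the first case only. An AE with a known pre-dose stop date and no onset information therefore meets the unconditional rule and nothing removes it.

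That result cannot be squared with the definition at the head of the section. An event that is over before the first injection can neither appear nor worsen after it.

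What is at stake is the accuracy of the TEAE tables in a study planned for about 30 patients (SAP 3.3), where one child is visible in a percentage. The TEAE flag also feeds the infection item among the inhibitor risk factors in SAP 6.2.2.4.

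**Working it through.** The plan states no figure on this point, so there is none to reproduce. The check applies the rules literally and then scales the result.

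**1. Can a pre-dose AE be on file?** Yes. Protocol 15.3.1 requires recording of "Any AE experienced by the subject between the time of signing of the ICF and the Safety Follow-up Visit", so collection starts at consent. Protocol 7.3.1 allows consent before birth. It also allows 8 weeks for screening assessments, and a further 8 weeks for those still outstanding.

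**2. What do the rules give?** Take four onset patterns and three stop dates. Partial onsets share the year, or the month and year, of the first dose. The full onset date is before the first dose, without worsening afterwards.

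| Onset date | Stop before first dose | Stop after first dose | Stop missing |
|---|---|---|---|
| Completely missing | TEAE | TEAE | TEAE |
| Year only | not TEAE | TEAE | TEAE |
| Month and year | not TEAE | TEAE | TEAE |
| Full date, pre-dose | not TEAE | not TEAE | not TEAE |

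In the first column the stop date is the same in every row, yet the first row has the opposite class. The only difference is whether any part of the onset was recorded.

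**3. Precedence.** The table lets the last rule win over the day-missing and month-missing rules. The SAP does not say so. It is the only reading that gives the last rule any effect: where those rules already return not TEAE, it changes nothing.

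**4. What does the correction change?** Extending the last rule to completely missing onsets alters 1 of the 12 cells: onset completely missing, stop before first dose. An unknown onset with a later or missing stop date stays a TEAE, so the cautious default is kept.

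**5. Reference point.** The definition counts from the first injection of rFIXFc; the last rule counts from the first dose of study drug. Protocol 7.1 allows up to 3 injections of commercial rFIXFc before eligibility is confirmed, so the two dates can differ for some children.

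**6. Size.** One child wrongly added to a row changes it by 100/N percentage points at most.

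- N = 30 (planned total): 100/30 = 3.3 points.
- N = 20 (assumed, for a smaller regimen column): 100/20 = 5.0 points.

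These are maxima. SAP 9.3.3 counts a patient once per system organ class or preferred term, so the increment is zero if the child has another event in that row. The documents do not allow an estimate of how many such records there will be.

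**The case against.** The strongest reply is that the definition governs and the list only settles doubt. A stop date before the first dose leaves no doubt, so a sensible programmer would exclude the event and read partial loosely, as covering wholly missing dates too. SAP 6.4.1 points the same way: it treats medications as concomitant unless they can be excluded. This may well be the intent, but it is not what 9.3.1 says. The section itself distinguishes partial from complete missingness, gives the complete case an unconditional rule, and states no precedence. Two programmers could produce different tables.

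The second reply is that the triggering record hardly exists, and much of this stands. Because AEs are recorded only from consent, an event that ended before dosing has an onset bounded by the consent date and its own stop date. Protocol 15.5.1 requires investigators to determine onset dates, and Protocol 18.3 provides for omissions to be resolved at monitoring visits. These controls make the case rare. They do not correct the rule if a record slips through, since the SAP imputes no onset date from those bounds.

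A reader might infer that serious event counts are inflated too. The documents do not support that as an expected effect. Protocol 15.1.2.1 gives serious events before any rFIXFc their own category with 24-hour reporting. Protocol 16.5.2.2 identifies them in the listing and limits summaries to serious events after the start of treatment.

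A reader might also infer that every misclassified child adds 3.3 points, or that such events will swell the Severe or Related rows. The first fails because of once-per-row counting. The second needs a further missing field on the same record, since only missing severity or relationship is assigned to those categories (SAP 9.3.5 and 9.3.6).

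Finally, the error would be visible. SAP 9.3 lists all AEs with resolution study days, so a recorded pre-dose stop date would show as a negative day even with the onset day blank.

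**Conclusion.** Wrong as written, and minor. The rule for a completely missing onset gives a result that the section's own definition rules out, and nothing elsewhere in the SAP corrects it.

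The size is at most 3.3 percentage points per misclassified child in an overall row. This assumes 30 dosed children and a child with no other event in that row. The direction is towards over-counting TEAEs, so no safety signal is hidden. The count of inhibitors, the primary endpoint, does not use the flag. A reader might take this as a threat to the trial's safety conclusions; the rarity of the record and the direction of the error do not support that.

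**What to change.** Reword the last rule of SAP 9.3.1 along these lines: *where the start date is partial or completely missing and the stop date is known to fall before the first injection of rFIXFc, the AE is not a TEAE; this takes precedence over the rules above.*

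Three things change: the rule covers completely missing onsets, its precedence is stated, and it uses the same reference point as the definition. The sponsor should also say whether that reference point includes commercial rFIXFc, so that the definition and the rule cannot diverge.

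The cost is a few words in the SAP and one condition in the derivation code. No data collection changes.

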### 9.3.2. Overall (Top-Line) Summary of Treatment-Emergent Adverse Events

A top-line summary of treatment-emergent adverse events (TEAEs) will be provided which tabulates the number and percentage of patients who experienced a TEAE, related TEAE, treatment-emergent SAE, or treatment-emergent related SAE; the number and percentage of patients who discontinued treatment and/or the study due to a TEAE; and the number and percentage of patients who died. This table will be presented by treatment regimen as described in Section 5.1.1.

This summary will also be presented by EPD entry compliance (see Section 6.6.2.3), <80% and >=80%, where >=80% is considered compliant.

### 9.3.3. Summary of Treatment-Emergent Adverse Events

The overall incidence of TEAEs will be summarized by SOC and preferred term. SOCs and preferred terms within each SOC will be presented alphabetically. For the purpose of

	Statistical Analysis Plan	Final v1.0
---	----------------------------------	-------------------

summarization, a patient is counted once in a SOC or preferred term if the patient reported one or more events in that SOC or preferred term. This table will be presented by treatment regimen as described in Section 5.1.1.

This summary will also be presented by EPD entry compliance (see Section 6.6.2.3), <80% and >=80%, where >=80% is considered compliant.

#### **9.3.4. Adverse Events in Descending Order of Incidence**

A table will be provided that displays AE preferred terms in descending order of incidence on the overall incidences. Only preferred terms will be included in this table (i.e., the display will not include SOCs).

A similar table will be provided for severe AEs. AEs for which the assessment of severity is missing will be included in this table.

#### **9.3.5. Severity of Adverse Events**

AEs are classified by the Investigator for severity (“Mild”, “Moderate”, and “Severe”). An overall summary of TEAEs by SOC, preferred term, and severity will be presented. AEs with a missing severity will be counted as “Severe” in the summary table. A patient will be counted once for each SOC and preferred term based on the greatest severity within that SOC and preferred term, respectively.

#### **9.3.6. Relationship of Adverse Events to Study Drug**

AEs are classified by the Investigator for relationship to study drug (“Not related” and “Related”). An overall summary of TEAEs by SOC, preferred term, and relationship will be presented. AEs with a missing relationship will be counted as “Related” in the summary table. A patient will be counted once for each SOC and preferred term based on the highest relationship within that SOC and preferred term, respectively.

#### **9.3.7. Serious Adverse Events**

Any AE reported as resulting in death, immediate risk of death (life threatening), inpatient hospitalization or prolongation of existing hospitalization, persistent or significant disability/incapacity, or a congenital/anomaly/birth defect will be classified as an SAE. An SAE may also be any other medically important event that, in the opinion of the Investigator, may jeopardize the patient or may require intervention to prevent one of the other outcomes listed above. Events considered medically important, as defined in Section 15.3.2 of the protocol, are also considered to be SAEs.

All SAEs will be listed; treatment-emergent SAEs will be summarized overall by SOC and preferred term.

#### **9.3.8. Adverse Events Leading to Treatment Discontinuation or Withdrawal From the Study**

	Statistical Analysis Plan	Final v1.0
---	----------------------------------	-------------------

AEs leading to treatment discontinuation or withdrawal from the study will be listed. All AEs reported on the AE log with “Was the patient terminated from this study due to this AE” as “Yes” or “Action Taken with Study Drug” with a response of “Drug Withdrawn” will be included.

### **9.3.9. Deaths on Study**

A listing of events leading to death occurring on the study will be provided.

### **9.3.10. Adverse events of Special Interest**

There are no specific AE outputs focusing on events of special interest. Any consideration of these will be based upon medical review of existing outputs.

## **9.4. Clinical Laboratory Evaluations**

All laboratory evaluations will be summarized for the Safety Analysis Set, as described in the rest of this section. Data collected at local laboratories will be excluded from analysis, unless otherwise specified. All laboratory data will be provided in data listings; abnormal values relative to laboratory normal ranges and potentially clinically significant abnormalities will be identified. Laboratory evaluations taken during major surgical/rehabilitation periods will not be included in any summary but will be included in the listings and flagged.

Laboratory values of the form “<x” (i.e., below the lower limit of quantification [LLOQ]) or “>x” (i.e., above the upper limit of quantification [ULOQ]) will be imputed as “x” in the calculation of summary statistics but displayed as “<x” or “>x” in the listings.

### **9.4.1. Hematology and Chemistry**

Hematology measurements that will be collected and summarized include: white blood cell count (WBC) and differential, red blood cell count (RBC), hemoglobin, hematocrit, and platelet count. Chemistry measurements that will be collected and summarized include: sodium, potassium, chloride, total protein, total bilirubin, gamma glutamyl transferase (GGT), aspartate aminotransferase (AST), alanine aminotransferase (ALT), alkaline phosphatase, blood urea nitrogen (BUN), serum creatinine, and glucose.

#### **9.4.1.1. Change from Baseline**

Hematology and chemistry results at baseline and post baseline visits, along with change from baseline, will be summarized with descriptive statistics by visit and for the end of study. Data from unscheduled visits will be excluded from this analysis. In the event of retests or repeat assessments at the same time point, the last non-missing evaluable measurement will be used for the purpose of analysis.

#### **9.4.1.2. Shifts**

Each patient’s laboratory values will be classified according to whether the test result is “low” (below the lower limit of normal [LLN]), “normal” (within the normal range), “high” (above the

upper limit of normal [ULN]). Shift tables will be constructed based on both the minimum and maximum post baseline values for each patient. Data collected from unscheduled visits will be included in the determination of the per patient minimum and maximum values.

A separate table will be provided which summarizes the results of the shift tables in which the number and percentage of patients with a shift to low (from normal, high, or unknown) and the number of patients with a shift to high (from normal, low, or unknown) will be tabulated; percentages will be based on the number of patients at risk. The number at risk for a shift to low (high) is the number of patients whose baseline value was not low (high), including unknown, who had at least one post-baseline value. Only directions of change indicating a clinical concern will be included in this table summarizing the shifts. The direction of concern is provided in [Table 1](#).

**Table 1: Direction of Change Indicating Clinical Concern for Laboratory Tests**

Laboratory Test	Direction	Laboratory Test	Direction
Chemistry		Hematology	
Liver		White blood cells	Low and High
ALT/SGPT	High	Lymphocytes	Low and High
AST/SGOT	High	Neutrophils	Low and High
ALP	High	Monocytes	Low and High
Total bilirubin	High	Eosinophils	Low and High
GGT	High	Basophils	Low and High
Renal		Red blood cells	Low and High
Blood urea nitrogen	High	Hemoglobin	Low and High
Creatinine	High	Hematocrit	Low and High
Electrolytes		Platelets	Low and High
Sodium	Low and High		
Potassium	Low and High		
Chloride	Low and High		
Other			
Glucose	Low and High		
Total protein	Low and High		

**9.4.1.3. Potentially Clinically Significant Laboratory Abnormalities**

Abnormal laboratory values will also be evaluated by determining the number and percentage of patients with at least one potentially clinically significant laboratory abnormality over the course of the study that also represents a change from baseline. The potentially clinically significant levels are based on Grade 2 or higher thresholds from the Common Toxicity Criteria for Adverse

Events (CTCAE v 4.02 2009) where possible, or were defined by Bioverativ’s Pharmacovigilance group..

Patients who have a post baseline laboratory value that meets the criteria for being potentially clinically significant but do not have a baseline value will be included in the numerator for determining the percentage of patients with an abnormality. Percentages will be based on the number of patients with at least one post baseline value for the given laboratory test. Threshold levels for potentially clinically significant laboratory abnormalities are provided in [Table 2](#) (hematology) and [Table 3](#) (chemistry). Data collected from unscheduled visits will be included in this analysis.

**Table 2: Threshold Levels for Potentially Clinically Significant Hematology Abnormalities**

	Low	High
Neutrophils	<1.5 x 10  /L	NA
Eosinophils	NA	>1.6 × 10  /L
Hemoglobin	<100 g/L	Increase in >20 g/L above ULN
Hematocrit	<30%	≥60%
Platelet count	≤75 x 10  /L	≥700 × 10  /L

NA = not applicable

**Table 3: Threshold Levels for Potentially Clinically Significant Chemistry Abnormalities**

	Low	High
Liver		
ALT/SGPT	NA	>3 × ULN
AST/SGOT	NA	>3 × ULN
Total bilirubin	NA	>1.5 × ULN
GGT	NA	>2.5 × ULN
Renal		
Creatinine	NA	>1.5 × ULN
Electrolytes		
Chloride	≤90 mmol/L	≥118 mmol/L
Other		
Glucose	<3.1 mmol/L	>8.9 mmol/L
Total protein	≤45 g/L	≥100 g/L

NA = not applicable, ULN = upper limit of normal

#### 9.4.2. Urinalysis

	Statistical Analysis Plan	Final v1.0
---	----------------------------------	-------------------

These assessments were not performed in this study.

### **9.4.3. Incidence of Inhibitor Development**

All the analyses in this section will be presented for the Safety Analysis Set. All analyses of, and derivations based upon, inhibitor test results are performed using the Nijmegen Inhibitor Fc assay and plasma derived (PD) assay.

#### **9.4.3.1. Endpoint Definition**

A positive inhibitor occurs where a patient has a value  $\geq 0.6$  Bethesda Units (BU/mL) confirmed on re-testing 2-4 weeks later. See Section 5.2.4 for exact definition. Results from blood samples collected during surgical/rehabilitation periods for the purpose of determining the presence of an inhibitor will be included in this analysis. Inhibitor test data will be listed for all patients.

#### **9.4.3.2. Primary Analysis**

The primary analysis of overall incidence of positive inhibitor formation will be based on all patients in the Safety Analysis Set. Any patient who develops an inhibitor following the initial rFIXFc administration will be included in the numerator. All patients who have received at least 1 dose of rFIXFc will be included in the denominator. An exact 95% confidence interval for the proportion of patients with a positive inhibitor will be calculated using the Clopper-Pearson method for a binomial proportion. PROC FREQ in SAS version 9.4 or higher will be used to produce this confidence interval.

The incidence of positive inhibitor formation will be summarized separately for the types of inhibitor specified in Section 5.2.4, namely:

- Patients with high-titer inhibitors
- Patients with low-titer inhibitors that meet the clinically meaningful criteria
- Patients with low-titer inhibitors that do not meet the clinically meaningful criteria

#### **9.4.3.3. Supporting Analyses**

To support the primary analysis results, the following will also be presented, using the primary methodology.

#### **Overall Incidence based upon ED Milestones**

The overall incidence of positive inhibitor formation will be presented for all patients who have reached at least 10, 20 and 50 EDs and had at least one inhibitor test performed at or beyond this milestone. For these analyses, any patient who develops an inhibitor following the initial rFIXFc administration will be included in the numerator and denominator. Patients who do not develop an inhibitor but reached the milestone number of EDs will be included in the denominator, i.e.,:

$$\text{Incidence rate} = \frac{\text{Number of patients with an inhibitor}}{\text{Number of patients reaching ED milestone or who have an inhibitor}}$$

	Statistical Analysis Plan	Final v1.0
---	----------------------------------	-------------------

